This proposed study addresses this call by testing the efficacy of a transformative patient-centric intervention designed to reduce the burden of NPS in Veterans with dementia who live at home with family caregivers. The innovative intervention, the Tailored Activity Program (TAP-VA), involves 8 sessions over 4 months in Veterans' homes. An occupational therapist conducts a systematic assessment to identify a Veteran's preserved capabilities and deficit areas, and previous roles, habits and interests from which to develop and introduce activities tailored to the Veteran's profile. Family caregivers are then trained to incorporate tailored activities into daily care routines. The intervention was pilot tested in an NIMH funded study with 60 community-living individuals with dementia. Findings from this pilot showed statistically significant and clinically meaningful reductions in NPS, specifically agitation and less time being on "duty" by family caregivers. Results of this pilot phase support moving forward with a full-scale Phase III efficacy trial. We plan to test TAP-VA in a randomized two-group parallel design in which 160 racially and ethnically diverse Veterans with dementia and their family caregivers (dyads) will be randomly assigned to receive TAP-VA or an attention control group. All dyads will be evaluated at baseline and 4-months (main trial endpoint), and then reassessed at 8-months to evaluate long-term treatment effects (baseline to 8 months), including continued activity use, caregiver well-being, and costs.

4. Background:

Over 5 million Americans have Alzheimer's disease or related dementias, a progressive and irreversible neurodegenerative syndrome, with prevalence rates expected to reach close to 16 million individuals by 2050. As populations age worldwide, dementia will increase dramatically and reach epidemic proportions. Among Veterans 65 and older, prevalence rates are similar to the population at-large with 7.3% having dementia across all races, except for African-Americans for whom the rate is 50% higher. Prevalence rates across VISNs range from 5.8 to 9.4% with dementia associated with substantially higher Inpatient and outpatient service utilization relative to other VA patients.

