Our long-term objective, if proven efficacious, is to integrate TAP-VA into standard care practices within the VHA system as the first treatment choice to address NPS in Veterans with dementia living at home. This would transform the current paradigm of dementia care which relies on pharmacologic management.

[figure not shown]
6. Research Plan:

Overview: This study will test whether a targeted Veteran-centric intervention reduces NPS (NPI total score of frequency by severity) and, secondarily, whether it reduces burden by reducing time spent in care, and enhancing skill in family caregivers. We also seek to evaluate its cost savings in terms of health care utilization rates of both Veterans and family caregivers using a cost diary. We will enroll 160 Veterans with dementia whose caregivers report one or more NPS and are living at

home. Veterans with diagnosis codes 290.0, 290.2, 290.3, 331.2 (senile dementias), 290.4 (vascular dementia), 294.8 (dementia not otherwise specified), 331.0 (Alzheimer's disease), 331.1 (frontotemporal dementia), and 331.82 (Lewy body dementia) will be considered to have dementia diagnoses and eligible for study participation. Veterans with these diagnostic codes will be recruited from NF/SG VHS Geriatric Research, Education & Clinical Center (GRECC) and Geriatrics and Extended Care Service (GECS) outpatient services, including the Home Based Patient Care (HBPC) and Homemaker Home Health Aide program.

Eligible dyads will receive a baseline home interview (T1), and then be randomized to experimental (TAP-VA) or attention-control group conditions. Experimental dyads will receive up to 8 contacts with an occupational therapist (OT) interventionist over 4-months whereas caregivers in the attention control group will receive bi-monthly telephone contact (up to 8 contacts) in which education is provided and tailored to address unmet expressed informational needs of caregivers. Information concerning the value of activity and a list of activity ideas will also be provided. All dyads will be retested at 4-months from baseline (T2), main study endpoint, and 8-months from baseline (T3) at home to evaluate long-term effects. Interviewers will be masked to treatment assignment throughout the study (Figure 1). Each study component is described in more detail below.

**FIGURE 1
FLOW CHART OF STUDY DESIGN**

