TAP provides caregivers with the requisite knowledge and skills to use activities. Caregivers are instructed in specific skills such as ways to simplify activities, the environment and their communication, and how to help the Veteran initiate and follow a sequence. The overall goal is to provide predictability, familiarity and structure in the daily life of Veteran and caregiver and establish a level of environmental stimulation appropriate to Veteran abilities. Three clinical elements are used to enhance caregiver receipt and enactment of intervention strategies: 1) the OT engages caregivers (vs being prescriptive), 2) the caregiver is provided repeated opportunities for practice and modification of techniques, and 3) the OT uses validation and actively demonstrates techniques within the context of their use. Caregivers are provided concrete knowledge as to what the Veteran is capable of doing (e.g., can grasp object such as a plate) and his/her specific limitations (e.g., needs verbal cueing to place dish in cabinet). With this knowledge, interventionists can help caregivers cognitively restructure their expectations, behavioral goals and reactions to the Veteran.

During treatment sessions, caregivers are taught to: 1) recognize capabilities and deficits, 2) translate capabilities into objective activity goals, and 3) generate specific steps to set up activities and help caregivers initiate/sequence.

7. Possible Discomforts and Risks:

This study involves the delivery of an online caregiving training and telephone support for CGs of elderly Veterans with dementia.

If a research staff member encounters a medical emergency over the telephone, we identify whether another individual is in the home, the person is put on hold and we call 911 immediately. If the situation occurs within the home, then the staff person calls 911 immediately, and stays with participant until help arrives. The PI is informed within 24 hours of the event. PI then contacts individual as a follow-up within two days. Research staff member completes alert form and provides to PI.

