If a research staff person encounters a situation in which the person (Veteran or CG) threatens to hurt self immediately, then staff person stays with person (on phone or in home), calls 911 and stays with individual until help arrives. If the person (Veteran or caregiver) is determined to not be an immediate threat to self, then the person is actively encouraged to contact physician or contact is made for the person if they allow that. An agreement is obtained with the person that they will not hurt themselves. The research staff person also informs the person that a member of the research team will be contacting him/her shortly to follow-up. Immediately at the conclusion of the interview, the PI is notified of the situation. The PI contacts the person to obtain further information and encourages immediate action be taken (e.g., physician referral). PI consults about case within 24 hours of event and consultation with the team's geriatrician will occur to review next steps. Research staff person involved fills out Alert form and provides to PI.

If caregiver scores in the high depressed range on the CES-D (>15 on 10-item version) in an interview, the PI contacts the caregiver to inform them of their elevated score and that they should follow-up with their physician. Consultation by the team's geriatrician will be obtained if necessary. Research staff person involved completes Alert form and provides to PI.

Evidence of physical abuse is as follows:

- 1) Caregiver or Veteran with dementia states to research staff that abuse occurs;
- 2) or research staff observes physical evidence (black eye, black and blue marks on arms/legs)

Research staff member informs participant that a senior member of the research team will contact him/her later that day. Staff member informs PI immediately upon completion of interview or intervention session. PI (or designate) contacts participant to obtain further information. Participant is strongly encouraged to call his/her physician and/or Adult Protective Services (phone number will be provided). Based on the situation, the PI may notify Adult Protective Services and consult with team's geriatrician. PI (or designate) completes Alert form.

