The DSMB will be responsible for reviewing the safety of study participants during the conduct of this study and provide recommendations to the research team on specific aspects of the research protocol as it pertains to safety, potential study alerts and adverse events. Specific responsibilities

of the DSMB will be to: a) provide an independent periodic review of recruitment and enrollment progress; b) review adverse events (AEs) including serious events and offer recommendations regarding the trial based on such observed events; c) serve in a consultative capacity to the research team regarding study procedures to address ethical dilemmas (e.g., reporting of abuse), safety of subjects in the trial, and appropriateness of all study procedures.

Composition of the DSMB: The DSMB will be an independent multi-disciplinary group consisting of biostatistical and research and clinical experts who collectively have experience in the treatment of depression, dementia and the environment, and the conduct and monitoring of randomized clinical trials that are community/home-based and nonpharmacologic. The 5-member board has no apparent conflict of interest with the study including financial, scientific or regulatory in nature. DSMB members are not employed by VHS and are not paid consultants on any related study of the principal investigator or that conducted by other members of the research team. DSMB members will be responsible for advising the principal investigator of any changes in their relationship and/or financial interests that occur during the course of the trial. The DSMB and PI will be responsible for deciding whether these changes create a conflict of interest. Any DSMB member who develops a conflict of interest during the course of the trial will be asked to resign from the DSMB and another person with similar areas of expertise will be sought. Otherwise, DSMB membership is to be for the duration of the trial.

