DSMB Meetings, Documentation: The DSMB will have one face-to-face meeting prior to entering into the field for the trial and one tele-conference call each subsequent year unless the DSMB decides otherwise at its first organizational meeting. More frequent meetings or teleconferences may be held to review serious adverse events from the trial at the discretion of the DSMB. At the initial meeting in year 01 (anticipated to occur in month 3 prior to entry into the field), the DSMB will review all study procedures including data collection forms, intervention protocol and oversight plan. At this meeting, the DSMB will agree on whether there should be interim analyses of efficacy endpoints and, if so, the stopping rules and interim analysis plan that avoids potentially biasing the investigative team. Modifications to protocols based on the DSMB review will be made prior to entering the field. At subsequent conference calls, the DSMB will review the progress of the study (accrual rate, protocol deviations and interim study analyses if recommended) and make recommendations. A representative of the research team will keep minutes of these meetings. A copy of the minutes approved by the DSMB will be shared with the IRB -01. The minutes will include recommendations of the DSMB. Meetings of the DSMB will be open unless the DSMB requests otherwise. A closed meeting of the DSMB may be requested if it is deemed necessary to review efficacy data. The DSMB chair or his/her designate will take meeting notes of closed sessions.

Provision of Data for DSMB Review: Interim Analyses: We have elected to not consider interim analyses in this study due to the extended time for recruitment and the low likelihood of a sufficiently large effect that would make it possible to stop early. However, we will revisit this decision with the DSMB at its first organizational meeting.

8. Possible Benefits:

Participants may learn about dementia and may be able to apply that knowledge in their daily CG activities. A better understanding of the responsibilities and varied activities of CGs of elderly Veterans with dementia will further research on the Veteran CG role: responsibilities, benefits and value.

9. Conflict of Interest:

There is no conflict of interest for the investigators.

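### Does the misworded opening of the risk section, combined with more home visits in TAP-VA, make the safety information unreliable between arms?

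*Protocol*

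**What the plan says.** Section 7 (Possible Discomforts and Risks) begins by stating "This study involves the delivery of an online caregiving training and telephone support for CGs of elderly Veterans with dementia". Section 8 (Possible Benefits) speaks to the caregiver's side: "Participants may learn about dementia and may be able to apply that knowledge in their daily CG activities".

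The design is described differently elsewhere. The Abstract says that TAP-VA "involves 8 sessions over 4 months in Veterans' homes". Section 6 says "Experimental dyads will receive up to 8 contacts with an occupational therapist (OT) interventionist over 4-months", while "caregivers in the attention control group will receive bi-monthly telephone contact (up to 8 contacts". Follow-up is common to both arms: "All dyads will be retested at 4-months from baseline (T2), main study endpoint, and 8-months from baseline (T3) at home". The interviewers are masked.

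Among the signs that Section 7 lists as evidence of physical abuse is that "research staff observes physical evidence (black eye, black and blue marks on arms/legs". Staff then notify the principal investigator once the interview or session is over. The investigator or a designate contacts the participant to learn more, acts according to the circumstances, and completes the Alert form. Later in Section 7, the DSMB's duties include reviewing adverse events, after which it may "offer recommendations regarding the trial based on such observed events".

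**The concern.** The opening sentence of Section 7 looks carried over from another study. No online training appears in either arm, and the experimental programme of home sessions is absent. In the text available, the section names no risk to the Veteran from doing the activities, although Section 6 gives physical examples such as cleaning windows.

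Two features then seem to combine:

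- The only heading under which an observed bruise appears is abuse, so a knock during an activity might be filed as abuse.
- A sign that staff must see depends on how often staff are in the home, and that differs sharply by arm.

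If the DSMB compared such alerts by arm, an effect of visit frequency could be read as harm from TAP-VA. Genuine activity injuries could not be separated from it. A later analysis could not repair this unless the detecting contact and the cause had been recorded.

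**Working it through.** The Protocol gives no figure of its own to reproduce on this point, so the check has four parts.

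**1. Do the rules in Section 7 depend on the wrong sentence?** The emergency rule covers events in the home as well as on the telephone. The self-harm rule does the same. The abuse rule refers to both interviews and intervention sessions. These rules fit the real design. Correcting the sentence would leave every one of them, and the number of home visits, unchanged.

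**2. Home contacts after baseline** (Abstract and Section 6):

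| Period | TAP-VA (maximum) | Control |
|---|---|---|
| Up to and including T2 | 8 + 1 = 9 | 0 + 1 = 1 |
| After T2, to T3 | 1 | 1 |
| Total | 10 | 2 |

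The ratio is 10/2 = 5. Counting telephone contacts as well, the maximum is 8 + 2 = 10 in each arm. The imbalance therefore concerns only what staff must see, not what they can be told, although control calls reach only the caregiver.

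**3. How large could the artefact be?** Assume that marks arise evenly over 8 months (34.8 weeks) at the same rate in both arms and stay visible for *w* weeks. Assume also that every visible mark is noticed, and that *k* therapist sessions are evenly spaced before T2 at 17.4 weeks. None of these inputs is in the Protocol. Then

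share seen = (total length of the union of the *w*-week windows before each home visit) / 34.8.

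| *k* | *w* (weeks) | TAP-VA | Control | Ratio |
|---|---|---|---|---|
| 8 | 1 | 10/34.8 = 0.287 | 2/34.8 = 0.057 | 5.0 |
| 8 | 2 | 19.4/34.8 = 0.557 | 4/34.8 = 0.115 | 4.8 |
| 8 | 3 | 20.4/34.8 = 0.586 | 6/34.8 = 0.172 | 3.4 |
| 8 | 4 | 21.4/34.8 = 0.615 | 8/34.8 = 0.230 | 2.7 |
| 4 | 2 | 12/34.8 = 0.345 | 4/34.8 = 0.115 | 3.0 |
| 2 | 2 | 8/34.8 = 0.230 | 4/34.8 = 0.115 | 2.0 |

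With 8 sessions and *w* = 2, the windows overlap before T2 because sessions are 17.4/9 = 1.93 weeks apart. The union is therefore 17.4 + 2 = 19.4 weeks. The Protocol sets an upper limit on sessions but no minimum, so 3 to 5 is not a bound.

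As an illustration in counts, take 80 per arm (160 split equally, an assumption) and an assumed 20% of Veterans with one mark, which gives 16 marks per arm. With *k* = 8 and *w* = 2, 16 × 0.557 = 8.9 would be seen in TAP-VA and 16 × 0.115 = 1.8 in control.

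**4. Would this count inform a decision?** In the DSMB text of Section 7, the observed events on which recommendations rest are the adverse events, including serious ones. Study alerts are named separately, and abuse reporting is placed under ethical dilemmas on which the board is consulted. No tally of abuse alerts by arm is planned in the Protocol. The board also reviews the data collection forms and the oversight plan before the trial enters the field.

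**The case for a change.** The strongest case for a change is that study alerts fall within the DSMB's remit by name, and a board overseeing a two-arm trial may well look at them by arm. Nothing in the Protocol warns that sightings are not comparable. Two extra fields on the Alert form (the contact at which a mark was seen, and its reported cause) would cost little, whereas information never recorded cannot be recovered. Comparing arms only at T2 and T3 would give 2 against 2 opportunities, both with masked interviewers.

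Part of this stands. The sentence is wrong, the 10-to-2 maximum is correct, and a naive count of sightings by arm would mislead.

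The rest does not. The Alert form is not shown, so it is a guess that it fixes an abuse label or lacks these fields. The investigator makes enquiries before the form is completed, so another cause can emerge. Because staff report at the end of an interview or a session, the type of contact can be known as well. The text available also omits consent pages, a usual place for listing risks, so the absence of an activity risk here is weak evidence that none is stated anywhere. A comparison limited to T2 and T3 would add an analysis that the Protocol does not plan. On the illustrative inputs it would rest on about 1.8 events per arm. How to tabulate safety data is ordinarily left to the statistical analysis plan.

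**Conclusion.** No change to the plan is needed. The first sentence of Section 7 conflicts with the Abstract and Section 6, and Section 8 is written around the caregiver although the primary aim concerns the Veteran. These are wording slips to reconcile at any routine edit. They alter nothing that the trial does, measures or concludes.

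The unequal chance of seeing a bruise is real: up to 10 home contacts against 2. It comes from comparing a home programme with a telephone control, not from the faulty sentence. On the assumptions shown, it could produce a ratio of sightings from 2.0 to 5.0 with equal true rates. It would mislead only in a by-arm count of abuse alerts, which the Protocol does not plan. A sensible analyst or board would read any such count with the difference in visits in mind. This conclusion rests on the Protocol alone; the forms and any statistical analysis plan were not available.

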These letters will request nursing staff and social workers to ask Veterans or their caregivers who might benefit from or be interested in this study to call the study team at the toll free number listed on the flyer.

Subject Accrual, Replacement Rule, Subject Attrition and Retention: *Subject Accrual:* Recruitment procedures will be implemented in month 6 of project year 01 and continue to month 3 of year 04 for a total of 33 months with close to 5 dyads enrolled per month. Based on our previous caregiver studies, the typical response rate from a targeted mailing to families is 10%; of responders, typically over 80% are eligible to participate in our studies that have similar enrollment criteria as that proposed for this trial. Thus, as shown in Table 1, even with one mailing from the two primary VA recruitment sources, we would be able to obtain our target sample size of 160 even when a conservative estimate of a 60% eligibility rate is applied. The numbers in the table were based on projections developed from actual new patients in each NF/SG VHS service over the past two years, with data provided by the GRECC. Thus, we do not anticipate difficulties obtaining the desired sample size dyads.

Techniques: The intervention is designed to tap into spared or residual abilities and provide an environment supportive of these abilities. The OTs select activities that build on preserved capabilities but do not tax areas of cognition that are most impaired (e.g., memory, new learning). In designing activities, OTs simplify activity and structure it to focus on single rather than multiple or complex tasks, thereby minimizing errors. The activity environment is set up to provide auditory or tactile cues to facilitate recall and guide initiation and sequencing. By grading activities to match the Veteran's capabilities, the OT minimizes demand that may heighten stress (e.g., high functioning individuals will be introduced to more goal-directed and multi-step activities, whereas lower functioning individuals will be introduced to activities that are based on repetitive motion (e.g., washing windows, folding towels) and integrate multi-sensory stimulation (e.g., soft music, objects pleasant to touch). Whereas previous activity interventions emphasized new learning, our approach does not, although it may entail some procedural learning if appropriate.

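### The rule for non-immediate self-harm treats a Veteran with dementia like a competent caregiver and never informs the live-in caregiver/LAR; for abuse, geriatrician consultation is only optional

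*Protocol*

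**What the plan says.** All the alert procedures are in Protocol section 7 (Possible Discomforts and Risks).

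**Self-harm, not immediate.** One rule covers Veteran and caregiver. On the person's own physician, it says that "the person is actively encouraged to contact physician or contact is made for the person if they allow that". It then adds: "An agreement is obtained with the person that they will not hurt themselves". The PI is told as soon as the interview ends, contacts the person and "encourages immediate action be taken (e.g., physician referral" being the example given. The PI must consult within 24 hours, and consultation with the team's "geriatrician will occur to review next steps". An Alert form is completed.

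**Abuse.** Evidence is either a statement by caregiver or Veteran that abuse occurs, or visible injury. The PI is informed, the PI or a designate contacts the participant, and the participant is urged to call a physician or APS. Beyond that, depending on the situation, "the PI may notify Adult Protective Services and consult with" the team's geriatrician.

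**Who the people are.** Section 6, Eligibility Criteria, enrols Veterans with a dementia diagnosis and lists an MMSE of 23 or less. The caregiver must live with the Veteran, and the same item lists LAR status.

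**The concern.** A rule built on encouragement, permission and a personal promise suits a caregiver with intact capacity. It suits a Veteran with dementia badly, because that person is asked to take in advice, act on it or consent to help, and keep a promise. A person who lives in the home and is listed as the Veteran's legal representative is left out of the sequence.

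What is at stake is participant safety, not the estimate of treatment effect. Every stated step can be completed after a Veteran voices a wish to self-harm without anyone who lives with or treats that Veteran being told. In the abuse rule, neither a clinical consultation nor a protective report is required, even when abuse of the Veteran is stated outright.

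**Working it through.** The protocol gives no figure to reproduce. The check sets the stated steps side by side.

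**1. Non-immediate self-harm, with the Veteran as the person at risk**

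| Step | Mandatory? | Depends on the Veteran? | Reaches own physician or caregiver/LAR? |
|---|---|---|---|
| Staff encourage physician contact, or make it if allowed | Encouragement yes, contact no | Yes | Physician only if the Veteran acts or allows it |
| No-harm agreement | Yes | Yes | No |
| PI notified | Yes | No | No |
| PI contacts the person and encourages action | Contact yes, action no | Action yes | Physician only if the Veteran acts |
| PI consultation within 24 hours | Yes | No | Not stated |
| Team geriatrician review | Yes | No | Possible as a next step, not stated |
| Alert form | Yes | No | No |

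The person's own physician comes up in 2 places (rows 1 and 4). Prompts that reach the physician without the person's action or permission: 0 of 2. Steps that inform the caregiver/LAR about the Veteran: 0. In this rule the caregiver appears only as another possible person at risk.

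**2. A case followed to the end.** Suppose a Veteran voices a wish to self-harm, is judged not to be in immediate danger, declines physician contact and agrees not to act. The PI is told, calls, encourages referral and consults; the geriatrician reviews; the form is filed. The rule has been followed in full, and nothing in it required telling the treating physician or the caregiver.

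**3. Comparison within section 7.** In the telephone medical-emergency rule, "we identify whether another individual is in the home". The idea of finding someone else in the home is therefore already in the section, but it is not carried into the self-harm rule.

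**4. Team geriatrician across the alert rules.** The role is named in 3 places:
- self-harm: mandatory;
- raised caregiver depression score: consultation by the team's "geriatrician will be obtained if necessary";
- abuse: under *may*, together with APS notice.

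That makes 1 mandatory + 1 if needed + 1 discretionary = 3. No reason is given for making the consultation optional for abuse when it is required for self-harm.

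**The case against.** The strongest reply is that a clinical safeguard is already mandatory. The PI must act, consultation must occur within 24 hours, and a geriatrician must review what to do next. Telling the physician or caregiver is a natural outcome of that review, nothing forbids it, and case-by-case disclosure respects the Veteran's privacy. This largely stands. It rules out any claim that the Veteran is left unprotected, and it argues against telling the physician in every case over the Veteran's refusal. It does not remove the gap, because the review is not required to consider either contact.

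Other points on that side:

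- *Capacity.* Section 6, Techniques, has therapists choose activities that "do not tax areas of cognition that are most impaired (e.g., memory, new learning". That concerns activity selection, not capacity to permit a call. Agreed: it shows what the team expects of these Veterans, and no more. Section 6, Recruitment Procedures, also provides for Veterans scoring above 23 on the MMSE, some of whom may well be able to decide.
- *Clinical links.* The main recruitment programs are directed by a co-investigator, so a clinical connection often exists. Names are removed and other facilities also refer, so this cannot be counted on for each Veteran.
- *Abuse.* The definition does not say who the victim is. It could cover a caregiver describing aggression by the Veteran, and aggressiveness is among the symptoms listed in section 4. Some discretion is therefore reasonable.
- *DSMB.* It reviews procedures before fieldwork and advises on reporting of abuse. It could correct the wording, but its role is consultative and is not protection in an individual case.

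A reader might infer three stronger things. The first is that a Veteran could go unseen for 4 months between assessments. That interval is the outcome schedule in section 6, whereas alert follow-up is separate and prompt. The second is that APS should be told on any statement of abuse. With the victim unspecified and PI inquiry already provided for, the text does not support an automatic trigger. The third is that the wording breaches a reporting law; the protocol cites none, so no such claim is made.

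**Conclusion.** The concern holds in a limited form. For a Veteran with dementia, the non-immediate self-harm rule rests on the Veteran's own promise and permission and leaves out the live-in caregiver/LAR. The mandatory PI contact, consultation and geriatrician review reduce that gap without closing it. For abuse, the weakness is that geriatrician consultation is discretionary where the parallel rule makes it mandatory, and that nothing says when APS must be told once inquiry leaves abuse of the Veteran open.

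The size is in the wording: 0 of 2 physician prompts independent of the person, 0 steps informing the caregiver/LAR, 1 of 3 geriatrician mentions mandatory. These counts describe the rules and are not a measure of risk. The protocol gives no alert rate, so no number of affected Veterans follows.

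The conclusion assumes that section 7 is the operative procedure. The Alert form is not shown and the consent pages were removed, so any disclosure terms there could not be judged. It also reads the eligibility item as making the caregiver the LAR. Immediate threats and the caregiver's own self-harm alerts are outside the point.

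**What to change.** 1. **Self-harm, Veteran branch.** When the person is the Veteran, the PI informs the caregiver/LAR unless there is evidence of abuse. The LAR's permission is enough for the team to contact the Veteran's physician. If the LAR cannot be told or refuses, the geriatrician consultation that is already mandatory decides, and records, whether to contact the physician without permission. The caregiver branch keeps its present wording.
2. **Evidence of abuse of the Veteran.** Make the geriatrician consultation mandatory (*will consult*). The PI notifies APS when abuse of the Veteran is not ruled out after the PI's inquiry and that consultation, without needing the caregiver's permission. PI inquiry still comes first, so bruising with an innocent cause need not be reported.

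The cost is a few sentences in section 7 and a line on the Alert form, with no added visits or participants. Section 6, Recruitment Procedures, already plans calls to the physicians of Veterans scoring above 23 on the MMSE, so a contact route exists for at least those. The downside is some loss of the Veteran's privacy and some reports that prove unfounded.
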